**Figure 3–1 Study Design: Study Periods and Visit Schedule**

Abbreviations: [REDACTED] BSL = Baseline; EOS = end of study; EOT = end of treatment; RAN = randomization; SOT = start of treatment.

\* Baseline assessments for fluorescein angiography, indocyanine green angiography, and color fundus photography will be collected at Screening (Visit 1) instead of Visit 2.

For subjects who used prohibited concomitant medications within 14 days prior to the planned randomization date, a washout period will be required prior to the first dose of study drug. The duration of this washout must be a minimum of 14 days for any prohibited ocular, nasal, and systemic medications (defined as those delivered by injection, oral, or transdermal methods) prior to the planned randomization date.

Approximately 35 subjects will be enrolled in the study. Once the Screening visit laboratory test results are confirmed, subjects who still meet all inclusion criteria and none of the exclusion criteria will be randomly assigned in a 3:3:1 ratio to receive one of the following treatment regimens:

1. MT-0814 [REDACTED] for 12 weeks (N=15)
2. MT-0814 [REDACTED] for 12 weeks (N=15)
3. Placebo [REDACTED] for 12 weeks (N=5)

[REDACTED]  
[REDACTED]  
[REDACTED]  
[REDACTED] Following training and under supervision, subjects will receive the first dose of study drug at the study site on Day 1 (Week 0). If a subject withdraws prematurely from the study before the completion of the treatment period (that is, before the Week 12 visit), a final visit must be scheduled for End of Study (EOS) assessments.

Efficacy, safety, and plasma concentration assessments will be performed as presented in the schedule of events (SOE) (Table 13–1); the plasma concentration sample collection schedule is presented in Table 13–2. Efficacy, safety, and plasma concentration measures are listed below.

- The primary efficacy measure is the assessment of change (from Baseline) in BCVA (measured by the Early Treatment of Diabetic Retinopathy Study [ETDRS]) at Week 12.
- The key secondary efficacy measure is the assessment of change (from Baseline) in the CSFT at Week 12.
- Additional efficacy/safety measures include assessment of the changes observed from Baseline at each visit for the following:

- Best-corrected visual acuity
- Central subfield thickness
- Optical coherence tomography (OCT) parameters

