## 7.4 Sample Size Calculations

The sample size for this study was not selected based on statistical power calculations, but rather on clinical considerations. Approximately 35 subjects will be randomly assigned (in a 3:3:1 ratio) to receive MT-0814 [REDACTED] MT-0814 [REDACTED] or placebo [REDACTED]. Randomization will be stratified by the BCVA score category (scores  $\leq 55$ , 56 to 70, or  $\geq 71$ ) observed for the subject's study eye on Day 1 (Baseline).

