## 7.9 Statistical Analysis Methodology

Statistical analysis will be performed using SAS software Version 9.4 or higher. Continuous variables will be summarized using the mean, standard deviation, median, minimum value, and maximum value. Categorical variables will be summarized using frequency counts and percentages. Data will be listed in data listings.

Details of the statistical analyses, methods, and data conventions are described in the statistical analysis plan (SAP).

All statistical tests will be 2-sided and performed using a 5% significance level, leading to 95% (2-sided) confidence intervals. Pairwise comparisons will be performed with no multiplicity adjustments. Additionally, no multiplicity adjustments will be performed for multiple endpoints.

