### **7.9.3 Analyses of Other Secondary Efficacy Endpoints**

Endpoints for changes from Baseline at each visit will be analyzed using an ANCOVA model, applying treatment as fixed effect and the parameter's Baseline value as the covariate, utilizing WOCF for missing data or treatment data occurring after receipt of rescue therapy. The t-tests will also be performed for changes from Baseline. Endpoints for proportions of subjects will be analyzed using Fisher's Exact test. Kaplan-Meier estimates will be presented for the time to receipt of rescue therapy.

Analyses will be performed separately to compare each dose of MT-0814 to placebo (eg, including only subjects receiving placebo and subjects receiving the MT-0814 dose being compared to placebo).

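### Fisher's Exact test for the proportion endpoints is valid but conservative at the planned 15 v 5 (maximum type I error 2.48% against a nominal 5%); a fully specified Boschloo test would recover some power at little cost

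*Combined protocol and SAP*

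**What the plan says.** Section 7.9.3 (Analyses of Other Secondary Efficacy Endpoints), repeated in the synopsis, states: "Endpoints for proportions of subjects will be analyzed using Fisher's Exact test". The same section adds: "Analyses will be performed separately to compare each dose of MT-0814 to placebo".

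Section 7.9 sets the level: "All statistical tests will be 2-sided and performed using a 5% significance level, leading to 95% (2-sided) confidence intervals". It also says: "Pairwise comparisons will be performed with no multiplicity adjustments", and it makes no adjustment across endpoints either.

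Section 7.4 gives the allocation: "Approximately 35 subjects will be randomly assigned (in a 3:3:1 ratio) to receive MT-0814". Section 3.1 lists the arms as 15, 15 and 5. Section 7.4 says that the sample size rests on clinical considerations and not on power. Section 4.2.4 rules out replacing withdrawn subjects.

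The proportion endpoints in Section 7.3 are dry retina at Weeks 4, 8, 12 and 16, need for rescue therapy, and BCVA gain or loss of 5, 10 or 15 letters at Week 12. The text does not discuss what error rate Fisher's test attains at these arm sizes, gives no expected event rates, and names no interval method for a difference in proportions.

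**The concern.** Fisher's test conditions on the total number of responders. With five placebo subjects, each total allows at most six tables, so the p-value moves in large steps and the 5% threshold usually falls well short of being used up. The test then works at a stricter level than the nominal one.

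Power is the scarce resource in a small proof-of-concept study. Dry retina in 8 of 15 on active (53%) and 0 of 5 on placebo would be reported as not significant, although another exact test with the same 5% guarantee would call it significant. The same loss can recur across all the proportion endpoints and both doses.

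**Working it through.** **Inputs.** n = 15 per dose and m = 5 on placebo (Section 3.1; 35 × 3/7 = 15 and 35 × 1/7 = 5). Two-sided 5% level, each dose separately against placebo (Sections 7.9 and 7.9.3). A table is (a, b): a responders of 15 on active and b of 5 on placebo, giving 16 × 6 = 96 tables.

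**Fisher p-value.** Given t = a + b responders in 20, P(b = k) = C(t,k)·C(20−t,5−k)/C(20,5), with C(20,5) = 15,504. The two-sided p sums all tables no more probable than the one observed.

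- (8,0): k = 0 has weight C(12,5) = 792 and k = 5 has C(8,5) = 56. k = 4 has 70 × 12 = 840, which exceeds 792 and is left out. p = 848/15,504 = 0.0547, not significant.
- (9,0): (462 + 126)/15,504 = 0.0379, significant.

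Against 0/5 Fisher therefore needs at least 9/15. Against 1/5 it needs at least 12/15, and against 5/5 at most 6/15.

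**True size of Fisher.** Size(p) is the sum over rejected tables of C(15,a)·C(5,b)·p^(a+b)·(1−p)^(20−a−b). Fisher rejects 26 tables. The maximum is at p = 0.5, where every outcome has weight 1/2^20. Thirteen tables favour active:

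- b = 0, a = 9 to 15: 5005 + 3003 + 1365 + 455 + 105 + 15 + 1 = 9949
- b = 1, a = 12 to 15: 5 × 576 = 2880
- b = 2, a = 14 and 15: 10 × 16 = 160

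Doubling for the mirror images, 2 × 12,989 = 25,978, and 25,978/1,048,576 = **2.48%**. At other common rates the size is 2.23% (40%), 1.78% (30%), 1.33% (20%), 0.49% (10%) and 0.10% (5%).

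**Boschloo.** The two-sided Fisher p is the ordering statistic, and its tail probability is maximised over the common rate. This keeps all 26 Fisher tables and adds six: (8,0), (13,2), (15,3) and their mirror images. At p = 0.5 the additions weigh 2 × (6435 + 1050 + 10) = 14,990. The size is (25,978 + 14,990)/1,048,576 = **3.91%**, which is also its maximum. The Boschloo p for (8,0) is 0.037.

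**Power at 15 v 5.** All rates are assumptions, written active v placebo.

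| Rates | Fisher | Boschloo |
|---|---|---|
| 50% v 10% | 18.5% | 30.1% |
| 60% v 10% | 39.0% | 49.6% |
| 10% v 60% (rescue-type) | 51.2% | 65.2% |
| 20% v 60% (rescue-type) | 30.2% | 39.1% |
| 30% v 10% | 0.9% | 3.1% |

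**Neighbouring arm sizes**, by the same enumeration. Power is Fisher to Boschloo.

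| Sizes | Fisher maximum size | 50% v 10% | 10% v 60% |
|---|---|---|---|
| 12 v 5 | 3.04% | 23.5% to 25.3% | 40.6% to 62.3% |
| 13 v 5 | 3.36% | 18.7% to 18.8% | 54.3% to 68.6% |
| 14 v 5 | 3.42% | 24.3% to 24.3% | 52.8% to 66.9% |
| 16 v 5 | 3.73% | 25.0% to 25.0% | 55.3% to 64.8% |
| 15 v 4 | 2.07% | 10.0% to 20.4% | 48.2% to 64.6% |
| 15 v 6 | 2.85% | 28.7% to 39.1% | 54.2% to 63.6% |

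At 14 v 4 Fisher's maximum is 2.00%. At every size checked, Boschloo rejects all the tables that Fisher rejects.

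**Which unconditional test.** Pooled-z Barnard at 15 v 5 adds only two tables, (0,2) and (15,3), and its size stays at 2.48%. Its next tied set, which includes (8,0), would bring the size to 5.01%. Power at 50% v 10% stays at 18.5%, and at 20% v 60% it moves from 30.2% to 31.0%. The two-sided rule matters as well: a Boschloo routine that doubles the one-sided p has size 3.71% and reaches only 31.1% at 20% v 60%.

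**The case against.** The best defence is that nothing is broken. The 5% in Section 7.9 is a ceiling and Fisher respects it. Any exact test on 96 tables falls short of 5%, Boschloo's included, and the choice between conditional and unconditional exact tests is a long-standing matter of preference. This stands: the point concerns lost power. A reader might infer that the plan breaches its own stated level, but a nominal level is met whenever the error does not exceed it.

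Second, the gains at low placebo rates belong to 15 v 5 and a few nearby sizes. Enrolment is only approximately 35 and withdrawals are not replaced, and one active subject more or fewer removes almost all of that gain. This stands too. A reader might take 2.5% as a general ceiling for this trial, and the neighbouring sizes do not support that. What survives is the rescue-type gain, roughly 7 to 22 points at 12 to 16 v 5 for 10% or 20% v 60%, and the fact that no size checked loses a rejection.

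Third, these are other secondary endpoints without multiplicity control, so a less strict test adds false positives. If gains and losses are tested separately there are 4 + 1 + 6 = 11 proportion tests per dose, or 22 in all. If every null held at a common rate of 50%, the expected number of false positives would be 22 × 2.48% = 0.55 with Fisher and 22 × 3.91% = 0.86 with Boschloo. This is a real but bounded cost.

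Finally, five placebo subjects limit the study far more than the test does. At 30% v 10% neither test is of any use.

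**Conclusion.** The point holds as an optional improvement. At the planned 15 v 5, Fisher's test is valid and conservative, with maximum size 2.48% against a nominal 5%. Boschloo's test, ordered by the two-sided Fisher p, has maximum size 3.91% and is never less powerful at any size checked. In the three main scenarios the gain at 15 v 5 is 11.6, 10.6 and 14.0 points (30.1 − 18.5, 49.6 − 39.0 and 65.2 − 51.2).

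The size figures need only the planned arm sizes and the stated level. The power figures rest on assumed rates and, at low placebo rates, on the arms being at or near particular sizes such as 15 v 5. A reader might also infer that any unconditional exact test gives the power back. Pooled-z Barnard does not in most scenarios at 15 v 5, so the test and its two-sided rule both have to be named. No primary or key secondary conclusion is affected.

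**What to change.** In Section 7.9.3 and the matching synopsis text, before unmasking, replace Fisher's test for all proportion endpoints (dry retina, rescue therapy, BCVA gain and loss) with Boschloo's unconditional exact test. State that it is two-sided, that the two-sided Fisher p-value is the ordering statistic, and that the tail probability is maximised over the common rate. Report exact unconditional 95% confidence intervals for the differences. Do not list Barnard's test as an interchangeable option.

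If Fisher is kept for familiarity, state its attained size at the planned arms so that a non-significant result is not over-read.

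The cost is a short text change, a less familiar test, and a check that the chosen software applies this two-sided rule; failing that, enumerating 96 tables is a small program. The other cost is somewhat more false positives across the unadjusted secondary tests, still at or below 5% for each. No extra subjects or visits are needed, and power will remain low with five placebo subjects.

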### 5.8.2 Prohibited Concomitant Medications, Treatments, and Procedures

[Note: "Systemic" drug/medication use is defined as any medication that may ultimately affect the eye (specifically the retina) and is delivered by injection or oral methods.]

Prohibited medications, treatments, and procedures during the study (Screening through EOS) are as follows:

1. Anti-vascular endothelial growth factor agents (systemic use or administered via intravitreal injection to the study eye).

Note: Injection of anti-VEGF into the fellow eye during the study period is prohibited. If the subject requires anti-VEGF treatment in the fellow eye, the subject should be discontinued from the study, and the EOT assessments should be completed.

- [REDACTED]
- [REDACTED]
5. Corticosteroids (systemic use or topical to the study eye, although topical dermal corticosteroid administration outside the periocular area is permitted per Exclusion Criteria 16 and 19).
    - a. Intravitreal injection of an ocular corticosteroid in the study eye within 12 months prior to Day 1 is exclusionary.
    - b. Sub-Tenon or subconjunctival injection of an ocular corticosteroid within 90 days of Day 1 is exclusionary. Systemic corticosteroid use by the subject within 28 days prior to Day 1 is exclusionary.
    - c. Topical dermal corticosteroid use by study subjects that has been administered outside of the periocular region is permitted prior to and during subject study participation.
  6. Photodynamic therapy (such as Vsudyne®), laser photocoagulation, radiation therapy, vitrectomy, or any other AMD treatment for the study eye.
  7. Cataract surgery, other ocular surgeries, and use of contact lenses (including therapeutic lenses) for the study eye.

The use of concomitant medication may be warranted for the treatment of AEs. The use of concomitant medications to treat an AE will be at the discretion of the investigator.

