### **7.3 Other Secondary Efficacy Endpoints**

The following secondary efficacy endpoints will be assessed:

- Changes from Baseline (Day 1) in BCVA by visit.
- Changes from Baseline (Day 1) in CSFT by visit.
- Proportions of subjects who achieve dry retina (defined in Sections 3.1 and 6.1.2) at Weeks 4, 8, 12, and 16.
- Changes from Baseline (Screening) in total lesion area (assessed via FA, ICGA, and CFP) at Week 12.
- Changes from Baseline (Screening) in CNV area (assessed via FA, ICGA, and CFP) at Week 12.
- Changes from Baseline (Screening) in leakage area (assessed via FA, ICGA, and CFP) at Week 12.
- Changes from Baseline (Screening) in polyp area (assessed via FA, ICGA, and CFP) at Week 12.
- Proportions of subjects who require rescue therapy (Section 4.2.3).

- Duration of time from Baseline (Day 1) to initiation of rescue therapy (Section 4.2.3).
- Proportions of subjects whose BCVA scores have increased/decreased by 5, 10, or 15 letters from Baseline (Day 1) to Week 12.

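### Time to rescue is a listed efficacy endpoint with no named between-arm comparison, and the only rescue test (Fisher on proportions) ignores timing and is very conservative at 15 v 5

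*Combined protocol and SAP*

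**What the plan says.** Section 7.3 has one rescue endpoint for the proportion, "Proportions of subjects who require rescue therapy", and a separate one for the time from Day 1 to the start of rescue.

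Section 7.9.3 assigns Fisher's Exact test to endpoints that are proportions. For the time endpoint it says "Kaplan-Meier estimates will be presented for the time to receipt of rescue therapy". It then says that each dose is compared with placebo separately, but names no method for comparing the curves. The synopsis has the same content.

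Section 7.9 sets the testing frame: "All statistical tests will be 2-sided and performed using a 5% significance level", and "Pairwise comparisons will be performed with no multiplicity adjustments". It leaves further methods and data conventions to a SAP, and no separate SAP text is in the supplied documents.

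On subjects who leave early:
- Section 7.5 keeps everyone randomised and dosed in the FAS.
- Section 4.2.4 bars replacement.
- Section 7.9.3 ties WOCF to change-from-Baseline endpoints only.
- Section 5.8.2 creates one route out without study-eye rescue: "If the subject requires anti-VEGF treatment in the fellow eye, the subject should be discontinued from the study".
- No section says how such a subject enters the rescue proportion, over what period rescue is counted, or when the Kaplan-Meier time is censored.

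**The concern.** Rescue means treatment failure and the end of study drug (Section 4.2.3). BCVA and CSFT values after rescue are replaced by WOCF, so whether and when a subject is rescued is evidence that needs no imputation. Subjects are seen weekly, so the timing is already collected.

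The plan makes timing an endpoint and then compares arms only on the proportion. A Week 1 rescue and a Week 11 rescue count the same. If most placebo subjects are eventually rescued, the proportion saturates and Fisher's test has little left to detect. The missing counting rules also leave the proportion and the curves open to more than one construction, to be settled later.

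**Working it through.** **Group sizes (plan's own figure).** 35 × 3/7 = 15, 35 × 3/7 = 15 and 35 × 1/7 = 5. This reproduces the 15/15/5 in Section 3.1, so each comparison is 15 v 5. The documents give no rescue rate, dropout rate or power; all such rates below are assumptions.

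**What Fisher's test can detect at 15 v 5 (two-sided 0.05, favouring drug).**

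| Placebo rescued | Most active rescues with p ≤ 0.05 | p there | p with one more |
|---|---|---|---|
| 2 of 5 | none | – | 0.053 (at 0 of 15) |
| 3 of 5 | 1 of 15 | 0.032 | 0.073 |
| 4 of 5 | 3 of 15 | 0.031 | 0.109 |
| 5 of 5 | 6 of 15 | 0.038 | 0.055 |

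Hand check of the first row: C(5,2)/C(20,2) = 10/190 = 0.053. With two or fewer placebo rescues, significance in favour of drug cannot be reached. Summing binomial probabilities over all significant tables gives a maximum true size of 0.0248, at a common risk of 50%.

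**Effect of dropout, if leavers are counted as not rescued.** With constant hazards, let h = −ln(1 − rescue risk) and d = −ln(1 − dropout risk), both over 12 weeks. The crude proportion is h/(h+d) × [1 − exp(−(h+d))]. Take a true risk of 60% in both arms, so h = 0.916:
- Dropout 30% (d = 0.357): 0.720 × 0.720 = 51.8%
- Dropout 10% (d = 0.105): 0.897 × 0.640 = 57.4%
- Dropout 5% (d = 0.051): 0.947 × 0.620 = 58.7%

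Dropout of 30% v 5% therefore shifts the proportions by 6.9 points in continuous time. Simulations with weekly visits gave 52–53% v 58–59%, about 6 points. Dropout of 30% v 10% gives 5 to 6 points. The shift favours whichever arm loses more subjects.

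Fisher's exact rejection rate with 30% active and 5% placebo dropout is 2.6–2.9% overall, depending on how weeks are rounded, with about 2% in favour of drug. Without dropout the figures are 2.2% and 0.8%. The error rate stays below 5%.

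**Power.** The comparator is a log-rank test permuted over all C(20,5) = 15,504 allocations. The model has constant hazards and weekly visits, with censoring at dropout or Week 12. Fisher is exact where there is no dropout and simulated otherwise; the log-rank results are simulated, mostly with 1,500 to 3,000 trials.

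| 12-week risk, placebo v active | Dropout, placebo v active | Fisher | Permutation log-rank |
|---|---|---|---|
| 30% v 10% | none | 10% | 13% |
| 40% v 20% | none | 10% | 16% |
| 60% v 30% | none | 16% | 24–25% |
| 60% v 20% | none | 30% | 41% |
| 80% v 40% | none | 24% | 39% |
| 80% v 30% | none | 41% | 56–58% |
| 90% v 30% | none | 61% | 75–77% |
| 95% v 50% | none | 24% | 58–59% |
| 60% v 30% | 10% v 30% | 19% | 24% |
| 60% v 20% | 30% v 10% | 20% | 41% |
| 80% v 30% | 30% v 10% | 26% | 48% |

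Null rejection of the permutation log-rank was about 4–6%; with 30% v 5% dropout, two runs gave 5.5% and 6.3%. The asymptotic log-rank reached 7% in one null scenario, so the permutation form is preferable.

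**Ceiling.** Schoenfeld's formula for 80% power is (1.960 + 0.842)² / [0.25 × 0.75 × (ln HR)²]. For 60% v 20%, HR = ln(0.8)/ln(0.4) = 0.244, so 7.85/(0.1875 × 1.996) = 21 events. The expected number is 5 × 0.6 + 15 × 0.2 = 6, and the pair has only 20 subjects.

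**The case against.** The strongest reply is that this is one of ten other secondary endpoints, in an explicitly unpowered proof-of-concept study with five placebo subjects and no multiplicity control. Showing Kaplan-Meier curves without a p-value is a legitimate choice there. Kaplan-Meier already uses timing and accommodates censoring, and a SAP, which Section 8 requires to be signed before database lock, may supply the rest. Part of the log-rank gain reflects Fisher's conservatism rather than timing. At milder risks the gain is only a few points, and either test would usually miss the effect. All of this stands, and it limits the weight of the point. It does not supply a comparison for an endpoint that the plan says it will compare.

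A reader might also infer more than the documents support:
- *Early leavers are counted as successes.* No section says so. It is a natural reading of a crude FAS proportion, but the actual gap is the absent rule.
- *Dropout could produce a false positive.* The shift is about 6 points under an assumed imbalance, one placebo subject is worth 20 points, and Fisher's error rate stays below 5%. With the imbalance reversed, the shift goes against drug.
- *Rescue is the trial's most sensitive efficacy signal.* Nothing in the documents shows this.
- *Fisher's test should be dropped.* It is prespecified for a separately listed endpoint. The observed proportion also needs no assumption about censoring as a description.

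**Conclusion.** The point holds in a limited form. Time to rescue is a secondary efficacy endpoint without a named between-arm test or effect measure. The one rescue test that is named ignores timing and runs at about half its nominal size. The denominator, time window and censoring rule are not stated in the supplied text.

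A permutation log-rank test would add roughly 5 to 22 points of power in most scenarios tried, about 35 points at 95% v 50%, and only 3 points at 30% v 10%. These gains rest on assumed rescue and dropout rates and on proportional hazards, the setting that suits the log-rank best. Power stays below 60% in all but the most extreme scenario tried. This is a worthwhile improvement to a secondary analysis and does not touch the primary endpoint.

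**What to change.** In Section 7.9.3, or in the SAP before database lock:

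1. Add a permutation (exact) log-rank test of time to rescue for each dose v placebo. State the set of allocations used; the figures here used all 15,504, whereas randomisation is stratified by Day 1 BCVA category.
2. Censor subjects who leave unrescued at their last assessment, and state one analysis window, for example Day 1 to Week 12. State the denominator for the proportion over the same window.
3. Report Kaplan-Meier rescue-free estimates with 95% confidence intervals by arm.
4. Keep Fisher's test on the proportion as a supporting analysis.

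The cost is a few sentences and a short program, with no new data. The downside is that censoring assumes leaving without rescue is non-informative, and the permutation test also relies on similar censoring between arms. Exits for adverse events or for fellow-eye anti-VEGF may break both assumptions, so unrescued exits should be tabulated by arm and reason beside the result.
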